5.4 Equipment

Postural outcomes will be measured on the Computer Assisted Rehab Environment (CAREN) (Motek Medical BV, Amsterdam) with integrated force plates. Spherical reflective markers placed bilaterally on anatomical landmarks will allow 3D-kinematic analysis with 7 MX-T20 optoelectronic cameras (Vicon, Oxford Metrics, UK), which will be done both online with D-Flow software (Motek Medical BV, Amsterdam) as offline. Changes in the brain hemoglobin concentrations will be registered with a wireless 16-16 fNIRS system (NirXsports 2), which has the required resolution and coverage to meet the study objectives. Sixteen optodes per hemisphere will be placed over the prefrontal, posterior parietal and premotor, SMA and M1 regions with an inter-optode distance of 35 mm, placed on an EEG-cap using the 10-20/10-10/10-5 EEG system.

6 Statistics, data handling and data management

6.1 Data storage

Part of the data that are obtained on paper will be stored on paper (e.g. questionnaires, informed consent forms), as well as in an excel file. The data obtained by computerized measures will all be stored in the original digital files, and the main variables will be stored in excel data files. All digital files will be saved on

protected server file storages of the KU Leuven (automatic back-up). Anonymized data files will be shared after publications of the results and upon request with the PI.

6.2 Data analysis and statistics

Calculation of the CoM data will be processed using Nexus 2.4 and customized Matlab scripts. Body movement during postural control, comprising CoM displacement, deviation of trajectory and speed will be calculated. To account for motion artefacts during fNIRS measurements, we will perform visual checks and signal processing techniques, including filtering and noise removal. A linear mixed model will analyze learning effects with training group as between-subject and pre-post-retention as within subject factor.

7 Safety

There are no permanent risks involved for the subjects participating in this study. All experiments are painless and harmless for participants. A safe and existing test infrastructure will be used and experienced researchers will conduct the experiments. Participants will be informed about the procedure and possible risks of the tests before the start of the experiment. Some of the participants may feel some fatigue during the weight shifting trials. To prevent excessive fatigue, participants will be encouraged to take breaks as needed in-between all trials. The fNIRS head cap will be cleaned/washed after each participant to ensure appropriate adherence to infection control policies. Based on a recent PhD thesis on the development and validity of the WASP task [de Vries, A (PhD thesis, March 2018)] we do not anticipate that any risks will be involved in the use of this WASP task.

For all subjects, a safety screening will be executed for the MRI protocol before informed consent will be obtained. Participants will be encouraged to ask questions about the study protocol and possible risks at any time of the experiment, as well as during the inclusion session. In between trials, sufficient rest periods will be inserted to avoid fatigue. During the MRI scan sessions, the aim is to minimize the potential discomfort of the participants. All subjects will be informed thoroughly about MRI technology and the setup in UZ Leuven Hospital. In addition, participants will be prepared for the real scanning session by including a practice session in a dummy MRI scanner. During the MRI scan session at the UZ Leuven Hospital, the researcher will be in contact (verbally) with the subject to assess his / her condition. An easily accessible panic button will be provided to all subjects and the function of this button will be explained in detail. The MRI scan sessions will be conducted by the researchers involved and will have no diagnostic purpose. Through the consent form, participants will be informed that the images will go through standard checks by a radiologist. Possible abnormalities can always be missed. If any deviations are detected, this will be reported to the Radiology Department of the UZ Leuven hospital, supervised by [name] and appropriate information will be delivered to the general practitioner involved.

7.1 Adverse event reporting

7.1.1 Definitions

- Adverse event (AE): any untoward medical occurrence in a patient or subject during an experiment, and which does not necessarily have a causal relationship with this treatment. An AE can be any unfavorable and unintended sign (including an abnormality on an MRI scan), symptom or disease temporally associated with the intervention, whether or not considered related to the

intervention. Any worsening (i.e., any clinically significant adverse change in the frequency or intensity of a pre-existing condition) should be considered an AE.

- Adverse Reaction (AR): any untoward and unintended responses to an investigational medicinal product or to an experiment and, when an investigational product is concerned, related to any dose administered.
- Serious adverse event (SAE): any untoward medical occurrence that results in any of the following:
 - Death
 - A life-threatening experience, i.e. in which the subject was at risk of death at the time of the event
 - In-patient hospitalization
 - A persistent or significant disability or incapacity
 - Important medical events that may be considered an SAE when, based on appropriate medical judgement, they may jeopardize the subject and may require medical or surgical intervention to prevent one of the above outcomes
- Suspected Unexpected Serious Adverse Reaction (SUSAR): an adverse reaction, the nature or severity of which is not consistent with the information on the experiment, and, when a clinical trial is concerned, with the applicable product information (e.g. investigator's brochure for an unauthorised investigational product or the patient leaflet joined to the summary of product characteristics for an authorised product).

7.1.2 *Adverse events that do not require reporting*

- Pre-existing conditions related to the symptomatology and medical treatment of Parkinson's disease, e.g. tremor, rigidity, balance impairments, freezing, orthostatic hypotension, etc.
- Pre-planned hospitalizations, unless the condition for which the hospitalization was planned has worsened from the first trial-related activity after the subject has signed the informed consent

7.1.3 *Recording and reporting of adverse events*

The investigators will seek information on AEs during each patient contact after the start of the intervention, i.e. at the end of day 1 and on day 2, by means of a safety assessment. All events, whether reported by the patient or noted by the trial staff, will be recorded within a reasonable time after becoming aware.

All AEs will be evaluated by an investigator as to:

- Seriousness: whether the AE is an SAE or SUSAR, see above for criteria
- Severity
 - Mild: no or transient symptoms, no interference with the subject's daily activities
 - Moderate: marked symptoms, moderate interference with the subject's daily activities
 - Severe: considerable interference with the subject's daily activities, unacceptable
- Causality
 - None: An AE which is not related to the study-related interventions

- Unlikely: An AE for which an alternative explanation is more likely (e.g. concomitant medication(s), concomitant disease(s)), and/or the relationship in time suggests that a causal relationship is unlikely
- Possible: An AE which might be due to the study-related interventions. An alternative explanation is inconclusive. The relationship in time is reasonable; therefore the causal relationship cannot be ruled out.
- Probable: An AE which might be due to the study-related intervention. The relationship in time is suggestive (e.g. confirmed by dechallenge). An alternative explanation is less likely.
- Definitely: An AE which is known as a possible adverse reaction and cannot be reasonably explained by an alternative explanation. The relationship in time is very suggestive (e.g. it is confirmed by dechallenge and rechallenge).

After informed consent has been obtained and after initiation of study-related interventions, all AEs, ARs, SAEs and SUSARs causally related to a study-related intervention will be reported until 30 days after the last study-related intervention or until last follow-up visit (whichever occurs first). All SAEs or SUSARs will be reported to the treating physician and ethical committee within 24 hours of the trial staff becoming aware of the event. Further study participation will be discussed with the treating physician. The immediate report shall be followed by detailed, written reports.

SAEs and SUSARs will be followed up until the outcome of the event and any related queries are resolved. Non-serious AEs and ARs will be followed up until the participants last study visit, and until all related queries have been resolved.

If the investigator becomes aware of an SAE with suspected causal relationship to the study-related interventions after the subject has ended the trial, the investigator will report this SAE within the same timelines as for SAEs during the trial.

7.1.4 Annual reporting

The sponsor has the obligation to, once a year throughout the clinical trial (or on request), submit a progress report to the ethical committee containing an overview of all serious adverse reactions that occurred during the reporting period and taking into account all new available safety information received during the reporting period.

8 Costs

Full reimbursement of travel expenses for the people with Parkinson's disease and age-matched controls (i.e. the healthy elderly) will be covered by the project. There will be no additional reimbursement.

9 Ethics

The protocol is submitted for review to the local Ethics Committee of KU Leuven (Commissie Medische Ethisch UZ Leuven, [name]). The study will be performed in accordance with The Code of Ethics of the World Medical Association (Declaration of Helsinki) and the principles of GCP. Any

subsequent protocol amendments will be submitted to the Ethics Committee and Regulatory Authorities for approval.

After complete explanation of the study protocol, written informed consent will be obtained from all participants prior to participation in the experiment.

The investigators will treat all information and data relating to the study confidential. If data are shared on the internet upon publications of the results, obligations with regard to protection of the results, confidentiality, security and the obligations to protect personal data will be guaranteed. Critical or sensitive data will be pseudonymized to ensure that re-identification by combining pseudonymized data with other population data is impossible. The key to the pseudonymized data will be stored on KU Leuven network drives, with no access from outside.

The collection, processing and disclosure of personal data, such as patient health and medical information is subject to compliance with applicable personal data protection and the processing of personal data (Directive 95/46/EC and Belgian law of December 8, 1992 on the Protection of the Privacy in relation to the Processing of Personal Data).

### **Study type**

Interventional

### **Brief summary:**

Older people show deficits in dynamic weight-shifting, as we found that more time is needed to perform weight-shifts and the movements become less fluent and accurate in older versus younger adults. Deficits with weight-shifting in the mediolateral (left-right) direction has been linked to balance and falls in ageing. Balance control can be improved with training. Virtual reality (VR) based training programs for improving balance are gaining ground, as it can provide both fun and challenging balance tasks, enhancing motivation. We demonstrated earlier that older adults show an overloaded neural activation pattern compared to young adults when performing the same VR-based mediolateral weight-shifting task (wasp game). What is yet unclear, is whether improved balance capacity can be gained with training and whether such an intervention impacts the underlying neural mechanisms. Using a combination of behavioral assessments and functional Near-Infrared Spectroscopy (fNIRS), the primary aim of this study is to investigate the effects of a VR-based weight-shift training and its underlying neural imprint in older adults. Furthermore, as our previous study also showed that adding an extra cognitive task in a so-called dual-task (DT) negatively affects weight-shifting performance, a secondary aim will be to test whether weight-shift training will enhance performance during such DT conditions. The results of this study may contribute to the future design of technology-based rehabilitation programs.

### **Primary outcome:**

For the primary behavioral outcome, weight-shifting speed in the mediolateral direction will be used. Participants will shift their weight to 80% of their stability limits within the Wasp Game. As people tend to slow down when reaching the 80% limit in order to aim for the wasp, mediolateral weight-shifting speed will be determined from the 80% limit on the right side the 80% limit on the left side and vice versa. Mediolateral weight-shifting speed will be determined and compared between the three test moments (pre, post, retention) and between the two groups (training, control) during the Wasp Game ST and DT.

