Recent systematic reviews showed that postural control in older adults can be improved with training¹⁵. However, little is known about the ability and maintenance of re-learning to weight-shift, let alone about its underlying mechanism. Therefore, the primary aim of this project will address this lacuna by studying the effects of training in weight-shifting performance in older adults and its underlying neural imprint. As our previous study (unpublished) showed that adding an extra cognitive task in a so-called dual-task (DT) negatively affects weight-shifting performance, a secondary aim will be to test whether weight-shift training will enhance performance during such DT conditions. The results of this study might form a basis for future technology-based rehabilitation programs.

4 Study objectives

The effects of postural learning on cortical activity have not been identified yet in older adults. During non-postural tasks, older adults needed greater activity and recruited more brain areas during automatization compared to young adults. This is suggested to be the primary reason for impaired motor automaticity with age¹⁶. We will use fNIRS to examine postural learning in the upright position for the first time in older adults. More specifically, we will investigate:

1. Changes in brain activity in frontal, (pre-)motor, and parietal regions associated with the acquisition and consolidation of weight shifting in older adults. In addition, as moving the Centre of Mass (CoM) deliberately also loads sensorimotor function, we will include the parietal cortex as region of interest.
2. Changes in brain activity in frontal, (pre-)motor, and parietal regions associated with the acquisition and consolidation of weight shifting compared to no training (control group).
3. Changes in brain activity in frontal, (pre-)motor, and parietal regions associated with the transfer of single-task acquisition and consolidation of weight shifting to dual-task weight shifting performance.

5 Methodology of the research

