5.1 Participants

In total, 40 subjects will be recruited aged 65+. Inclusion criterion include being able to independently stand upright > 5 min. Exclusion criteria are: (a) history of neurological disorders; (b) balance impairments (i.e. vestibular disorders); (c) cognitive impairment (Mini Mental State Exam (MMSE) < 24); (d) visual impairment precluding following of visual targets or colour-blindness as measured with the Ishihara test for color deficiency; (e) chronic musculoskeletal (e.g. osteoarthritis, osteoporosis), cardiovascular (e.g. hypertension, peripheral vascular disease) and respiratory (e.g. chronic obstructive pulmonary disease) disease, as well as diabetes related polyneuropathy.

For this study, 40 healthy older adults will be included. Our previous fNIRS study (unpublished) revealed that our primary outcome, weight-shifting speed, improved from $0,0668 \pm 0,0255$ m/s to $0,0916 \pm 0,0350$ m/s. Based on Caljouw et al.¹⁷, we expect a training effect size of 20%, resulting in a weight-shifting speed of $0,1094 \pm 0,0418$ m/s. Applying a power of 80% and alpha of 0.05 for a repeated measures ANOVA with a within-between interaction design (within: pre vs post: between: training vs control) we calculated a total sample size of 40 participants (20 per group). Considering possible data exclusion due to fNIRS measurements, the collected fNIRS data will be monitored during recruitment, and recruit more participants if necessary.

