### **Main analysis:**

Primary, secondary and tertiary outcomes will be compared between training and control group and pre, post and retention test using linear mixed models. We will determine the best model based on standard fitting criteria. . We will consider cognitive and balance skills as possible covariates, depending on between group differences and determined by a blind review of the data. Post-hoc testing will be corrected for multiple testing by Bonferroni corrections.

Depending on data normality, Pearson and/or Spearman correlation analysis will be performed between neural and behavioral outcomes within groups and test moments. Bonferroni corrections for multiple testing will be applied when necessary.

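### The SAP lists single-task and dual-task speed together as the primary outcome over three test moments, although dual task is a secondary aim and the sizing rests on one pre-post interaction

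*SAP*

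**What the plan says.** - **Outcome.** The SAP, under Primary outcome, states "For the primary behavioral outcome, weight-shifting speed in the mediolateral direction will be used". Speed is then to be "compared between the three test moments (pre, post, retention) and between the two groups (training, control) during the Wasp Game ST and DT". The two tasks are not ranked.
- **Aims.** The SAP's Brief summary says that "a secondary aim will be to test whether weight-shift training will enhance performance during such DT conditions". The last paragraph of Protocol section 3 ranks it the same way. Objective 3 in Protocol section 4 treats DT as transfer, covering brain activity "associated with the transfer of single-task acquisition and consolidation of weight shifting to dual-task weight shifting performance"; that objective itself states no rank.
- **Sizing.** Protocol section 5.1 starts from an unpublished study which "revealed that our primary outcome, weight-shifting speed, improved from" 0.0668 to 0.0916 m/s. It expects 0.1094 m/s with training and derives 40 participants at 80% power and alpha 0.05 for a repeated measures ANOVA "with a within-between interaction design (within: pre vs post: between: training vs control". Retention and task are not in that calculation, and the task behind the speeds is not given.
- **Analysis.** Protocol section 6.2 and the SAP's Main analysis plan linear mixed models of group by pre, post and retention. The SAP adds "We will determine the best model based on standard fitting criteria" and "Post-hoc testing will be corrected for multiple testing by Bonferroni corrections".

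**The concern.** The section that should fix the primary question holds two task conditions and three test moments, while the aims give one task priority and the sizing uses two moments.

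Training uses the weight-shifting game and DT is tested as transfer, so an effect in ST without one in DT, or the reverse, is plausible. In either case the SAP does not say whether the trial has answered its primary question. The choice could then be made after the results are seen, and the undivided 5% used for sizing would not be guaranteed.

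The Bonferroni sentence closes only part of the gap. If task is a factor in one model, task-specific contrasts are post-hoc and fall under it, but the decisive term is still not named. If ST and DT are modelled separately, each group-by-time test is a main test, and the rule does not govern the choice between them.

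**Working it through.** **1. The sections side by side**

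| Source | Task | Moments | Alpha |
|---|---|---|---|
| Protocol 3 and SAP Brief summary (aims) | DT is secondary | maintenance is part of the motivation (Protocol 3) | not given |
| Protocol 4 (objectives 1 and 2) | not given | acquisition and consolidation | not given |
| Protocol 5.1 (sizing) | not given | pre, post | 0.05, not split |
| Protocol 6.2, SAP Main analysis | not given | pre, post, retention | Bonferroni for post-hoc tests |
| SAP Primary outcome | ST and DT, unranked | pre, post, retention | not given |

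The last row disagrees with the first on task and with the third on moments.

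**2. Reproducing N = 40**

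Inputs from Protocol 5.1: 0.0916 (SD 0.0350) and 0.1094 (SD 0.0418) m/s, 80% power, alpha 0.05. Assumed, because not stated: f = d/2 and a pre-post correlation of 0.5.

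- Pooled SD = sqrt((0.0350² + 0.0418²)/2) = 0.0386
- d = (0.1094 − 0.0916)/0.0386 = 0.462, so f = 0.231
- λ = f² × N × 2/(1 − 0.5) = 0.231² × 40 × 4 = 8.53, with 1 and 38 df
- Power is 81.2% at N = 40 and 79.1% at N = 38

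So N = 40 reproduces, for one pre-post interaction tested once at 5%.

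**3. False-positive rate if either task may count**

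Two separate tests at two-sided 5%, bivariate normal, between-task correlation assumed:

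- correlation 0: 1 − 0.95² = 9.75%
- correlation 0.5: 9.1%
- correlation 0.9: 7.0%

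With one named ST test the rate is 5%.

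**4. Power of the options at N = 40, on the basis of step 2**

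- ST, pre to post, 5%: 81.2%.
- ST, omnibus over three moments (2 and 76 df, compound symmetry): λ = 8.53 × SS/0.5, where SS is the sum of squares of (0, 1, k) about their mean and k is the share of the gain kept at 24 h. For k = 0.5, SS = 0.5, λ = 8.53 and power is 72.9%. For k = 0 or 1, SS = 2/3, λ = 11.37 and power is 85.0%.
- Both tasks primary, each at 2.5%: 72.0% per task; N = 48 gives 80.8%.
- Both tasks primary under Holm (simulated): ST power is 76% to 79% if DT has the same effect, and 72% if DT has none.

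**5. Sensitivity**

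With pre-post correlation 0.3 or 0.7 in place of 0.5, the pre-post test has 67% or 96% power. The omnibus test with half the gain retained has 57% or 92%. If the groups are equal at pre and differ only at post, f = d/4 and the pre-post test has 29.6% power. These swings are larger than most differences between the options, so step 4 is useful only for comparing them.

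**The case against.** **The documents already point to an answer.** DT is ranked second in both documents, the sizing names the pre-post group interaction, and both analysis sections give group by time. The ST/DT phrase may also be descriptive: a near-identical closing formula appears for the HbO2 and HHb outcomes, and one variable can serve a primary aim in ST and a secondary aim in DT. Much of this stands. It would be wrong to say that the plan gives no indication of the leading task or term. But the primary outcome section does not state this reading, DT speed is absent from the SAP's secondary outcomes, and the conflict between two and three moments remains.

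**A reader might infer that the plan has a 7% to 10% false-positive rate.** The documents do not support that. It needs separate models and a rule that success in either task counts. Neither is stated, and the second runs against the ranking of the aims.

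**A reader might go further** and count pre-post and pre-retention contrasts in both tasks, giving 1 − 0.95⁴ = 18.5% for four independent tests. That is not supported either. One omnibus group-by-time test over three moments adds no inflation, and contrasts made after it fall under the Bonferroni rule.

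**Pre-post should not be imposed as the only choice.** This stands. Maintenance and consolidation are part of the protocol's rationale and objectives, so retention has a fair claim to a place in the primary test.

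**Conclusion.** The concern holds in a limited form. The SAP's primary outcome section conflicts with the plan's own ranking of aims on task, and with the sizing on test moments. As written, the plan can deliver two unranked primary results with no rule between them. The firm consequence is one of interpretation: if ST and DT disagree, the plan does not say which result decides.

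The 7% to 10% is a worst case under two unstated conditions and an assumed correlation. It should be fixed before the outcome data are examined, and a change of wording is enough.

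Nothing here validates N = 40. That figure reproduces with f = d/2 and a pre-post correlation of 0.5, neither of which the protocol states.

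**What to change.** In the SAP's primary outcome section:

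1. Make mediolateral speed in the Wasp Game ST the primary outcome, and move speed in the Wasp Game DT to the secondary outcomes.
2. Name one primary group-by-time test in ST at two-sided 5%. The sponsor chooses between the pre-to-post contrast, which matches Protocol 5.1, and one omnibus test over pre, post and retention, which matches the aims in Protocol 3 and 4, Protocol 6.2 and the SAP's Main analysis.
3. Confirm that the speeds in Protocol 5.1 are ST speeds.

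If the sponsor wants both tasks primary, control the overall error at 5% (Holm, for example) and restate the power.

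**Cost.** The change is to wording only. DT and retention are still analysed and reported, but a DT-only result no longer counts as a positive primary result. The pre-post choice adds no sample-size demand. The omnibus choice keeps N = 40 with about 73% to 85% power on the same assumed basis, depending on how much of the gain is retained, so the sponsor should state the retention pattern it expects. Under Holm on both tasks, N = 44 gives ST power of 80% to 83% if the effects are equal, and about N = 48 is needed if DT has no effect.
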